7. PLANNED ANALYSIS

The format of the listings and tables will follow the BI guideline "Reporting of clinical trials and project summaries" ([5](#)).

The individual values of all subjects will be listed. Listings will generally be sorted by dose group, subject number and visit (if visit is applicable in the respective listing). AE listings will be sorted by assigned treatment (see [Section 7.8.1](#) below for details). The listings will be contained in Appendix 16.2 (SDL) of the CTR.

The following standard descriptive statistical parameters will be displayed in summary tables of continuous variables:

N	number of non-missing observations
Mean	arithmetic mean
SD	standard deviation
Min	minimum
Median	median
Max	maximum

For plasma concentrations as well as for all PK parameters the following descriptive statistics will additionally be calculated:

CV	arithmetic coefficient of variation
gMean	geometric mean
gCV	geometric coefficient of variation

For PK parameters the following descriptive statistics will additionally be calculated:

P10	10 th percentile
Q1	1 st quartile
Q3	3 rd quartile
P90	90 th percentile

The data format for descriptive statistics of plasma concentrations will be identical to the data format of the respective concentrations. The descriptive statistics of PK parameters will be calculated using the individual values with the number of decimal places as provided by the evaluation program. Then the individual values as well as the descriptive statistics will be reported with three significant digits in the CTR.

Tabulations of frequencies for categorical data will include all possible categories and will display the number of observations in a category as well as the percentage (%) relative to the respective treatment group. Percentages will be rounded to one decimal place. The category missing will be displayed if and only if there actually are missing values. Percentages will be based on all subjects in the respective subject set whether they have non-missing values or not.

7.1 DEMOGRAPHIC AND OTHER BASELINE CHARACTERISTICS

Only descriptive statistics are planned for this section of the CTR. These will be based on the TS.

7.2 CONCOMITANT DISEASES AND MEDICATION

Concomitant diseases will be coded according to the most recent version of MedDRA. Concomitant medication will be coded according to the World Health Organisation – Drug Dictionary, version March 2018.

Only descriptive statistics are planned for this section of the CTR based on the TS.

A medication will be considered concomitant to a treatment, if it

- is ongoing at the time of first administration of the respective treatment or
- starts within the analysis phase of the respective treatment (see [Section 6.1](#) for a definition of treatments and analysis phases).

7.3 TREATMENT COMPLIANCE

Treatment compliance will not be analysed as a specific endpoint. Any deviations from complete intake will be addressed in the RPM/DBLM (cf. [Section 6.2](#)) and described in the CTR.

7.4 PRIMARY ENDPOINT

Refer to [Section 7.8.1](#) for a description of the analysis of AEs, and in particular the analysis of the number of subjects with drug related AEs, which is the primary endpoint of this trial.

7.5 SECONDARY ENDPOINTS

7.5.1 Key secondary endpoint

Not applicable.

7.5.2 Secondary endpoints

The analysis of secondary endpoints will be based on the PKS.

Dose proportionality will be evaluated as defined in the CTP, Section 7.3.2, by use of the power model for the secondary endpoints AUC_{0-12} , C_{max} , $AUC_{t,ss}$ and $C_{max,ss}$ of BI 1265162 in plasma.

Exclusion of PK parameters

The ADS ADPP contains column variables APEXC and APEXCO indicating inclusion/exclusion (APEXC) of a PK parameter and an analysis flag comment (APEXCO). All analyses based on the PKS are based on PK parameter values which are not flagged for exclusion, i.e. with APEXC equal to "Included".

Exclusion of plasma concentrations

The ADS ADPC (PK concentrations per time-point or per time-interval) contains column variables ACEXC or ACEXCO indicating inclusion/exclusion (ACEXC) of a concentration and an analysis flag comment (ACEXCO). Exclusion of a concentration depends on the analysis flag comment ACEXCO. For example, if ACEXCO is set to "ALL CALC", the value will be excluded for all types of analyses based on concentrations. If ACEXCO is set to "DESC STATS" the value will be excluded from descriptive evaluations per planned time point/time interval. If ACEXCO contains the addition "TIME VIOLATION" or "TIME DEVIATION", the value can be used for further analyses based on actual times. If ACEXCO is set to "HALF LIFE", the value will be excluded from half-life calculation only; the value is included for all other analyses. Excluded concentration itself will be listed in the CTR associated with an appropriate flag.

Further details are given in "Noncompartmental Pharmacokinetic / Pharmacodynamic Analyses of Clinical Studies" (4) and "Description of Analytical Transfer Files and PK/PD Data Files" (6).

7.7 EXTENT OF EXPOSURE

Only descriptive statistics are planned for this section of the CTR.

7.8 SAFETY ANALYSIS

All safety analyses will be performed on the TS.

7.8.1 Adverse events

AEs will be coded with the most recent version of MedDRA.

The analyses of AEs will be descriptive in nature. All analyses of AEs will be based on the number of subjects with AEs and not on the number of AEs.

For analysis, multiple AE occurrence data on the eCRF will be collapsed into one event provided that all of the following applies:

- All AE attributes are identical (lower level term, intensity, action taken, therapy required, seriousness, reason for seriousness, relationship, outcome, AESI)
- The occurrences were time-overlapping or time-adjacent (time-adjacency of two occurrences is given if the second occurrence started at most 1 hour after the first occurrence ended)

For further details on summarization of AE data, please refer to "Analysis and Presentation of Adverse Event Data from Clinical Trials" ([7](#)) and "Handling of missing and incomplete AE dates" ([3](#)).

The analysis of AEs will be based on the concept of treatment emergent AEs. That means that all AEs will be assigned to the screening or on-treatment phase as defined in [Section 6.1](#). AEs will be analysed based on actual treatments, as defined in [Table 6.1: 1](#).

An overall summary of AEs will be presented. This overall summary will comprise summary statistics for the class of other significant AEs according to ICH E3 ([8](#)) and for the class of AESIs.

CTP: *The following are considered as AESIs:*

Hepatic injury

A hepatic injury is defined by the following alterations of hepatic laboratory parameters:

- *AST (aspartate transaminase) and/or ALT (alanine aminotransferase) ≥ 3 -fold ULN combined with an elevation of total bilirubin ≥ 2 -fold ULN measured in the same blood sample, or*
- *aminotransferase (ALT, and/or AST) elevations ≥ 10 fold ULN.*

The investigator had to classify on the eCRF whether an observed AE was an AESI or not.

According to ICH E3 ([8](#)), AEs classified as "other significant" need to be reported and will include those non-serious and non-significant AEs

- (i) which are marked haematological or other lab abnormalities, or

- (ii) which were reported with "action taken = discontinuation" or "action taken = reduced", or
- (iii) which lead to significant concomitant therapy as identified by the Clinical Monitor/Investigator at a Medical Quality Review Meeting.

The frequency of subjects with AEs will be summarised by treatment, primary SOC and preferred term. AEs which were considered by the investigator to be drug related (primary endpoint) will be summarised separately. Separate tables will also be provided for subjects with SAEs, subjects with AESIs and subjects with other significant AEs (according to ICH E3 (8)). The frequency of subjects with AEs and the frequency of subjects with AEs considered by the investigator to be drug related will also be summarised by maximum intensity, primary SOC and preferred term.

The system organ classes and preferred terms within system organ classes will be sorted by descending frequency overall treatment groups.

For disclosure of AE data on ClinicalTrials.gov, the frequency of subjects with non-serious AEs occurring with an incidence of greater than 5 % (in preferred terms) will be summarised by treatment, primary SOC and preferred term. The frequency of subjects with SAEs will also be summarised.

For disclosure of AE data in the EudraCT register, the frequency of AEs, the frequency of non-serious AEs with an incidence of greater than 5 % (in preferred terms) and the frequency of SAEs will be summarised.

For support of lay summaries, the frequency of subjects with drug-related SAEs will be summarised by treatment, primary system organ class and preferred term.

7.8.2 Laboratory data

The analyses of laboratory data will be descriptive in nature and will be based on BI standards "Display and Analysis of Laboratory Data" (9).

Analyses will be based on normalised values, which means transforming to a standard unit and a standard reference range. The original values will be analysed if the transformation into standard unit is not possible for a parameter.

Descriptive statistics of laboratory values over time and for the difference from baseline (see [Section 6.7](#)) will be provided. For urine electrolytes (including potassium-creatinine quotient and sodium-creatinine quotient), the time matched change from baseline is analysed. In addition, median urine and serum electrolytes over time will be presented graphically. The graphics will also be prepared for the ratio of sodium / potassium in urine. Frequency tables of changes between baseline and last value on treatment with respect to the reference range will be presented.

Possibly clinically significant abnormal laboratory values are only those identified either in the Investigator's comments or at the RPM/DBLM at the latest. It is the Investigator's responsibility to decide whether a lab value is clinically significant abnormal or not. Standard or project-specific rules for flagging clinically significant values in an automated manner will not be applied in this study.

Clinically relevant findings in laboratory data will be reported as baseline conditions (at screening) or as AEs (during the trial) if judged clinically relevant by the investigator, and will be analysed as such.

Exposure-response analysis

The relationship between BI 1265162 plasma concentrations and serum potassium and sodium difference from baseline (see [Section 6.7](#)) will be analysed descriptively. Scatterplots of plasma concentration versus lab parameter will be prepared by dose groups. All time points with available lab data and valid time-matched plasma drug concentrations will be included. The following time points are matched time points for serum electrolytes and drug concentration: Day 1 2:00, Day 2 23:55, Day 8 07:55 and Day 8 10:00.

For the handling of missing values, see [Section 6.6](#). The placebo subjects will not be included in this analysis.

The relationship between the amount of BI 1265162 that is eliminated in urine during a 12h interval and urine potassium and sodium change from baseline will be analysed similarly. The following time points are matched time points for urine electrolytes and amount of eliminated BI 1265162: Day 1 08:00 to 20:00, Day 5 08:00 to 20:00, and Day 8 08:00 to 20:00.

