1.2.5 Clinical experience in humans

c15848749-03 Trial Protocol

04 Jul 2018

Page 21 of 84

c15848749-03

04 Jul 2018

Page 22 of 84

Proprietary confidential information © 2018 Boehringer Ingelheim International GmbH or one or more of its affiliated companies

Trial Protocol

04 Jul 2018

Trial Protocol

Page 23 of 84

Proprietary confidential information © 2018 Boehringer Ingelheim International GmbH or one or more of its affiliated companies

Systemic ENaC inhibitors such as amiloride have been used for years as potassium sparing diuretics in the treatment of hypertension, congestive heart failure and cirrhotic ascites. The side effect profile is well documented. Amiloride is normally well tolerated and, except for hyperkalaemia, significant side effects are infrequent. Nausea, anorexia, abdominal pain, flatulence and mild skin rashes are considered potentially related to amiloride but other side effects are generally associated with diuresis.

In addition there are clinical data of inhaled ENaC inhibitors administered to healthy volunteers and patients with cystic fibrosis for up to 6 months [R15-5485, R15-5349, R15-5599, R15-5505]. Phase II studies with competitor ENaC inhibitors are ongoing. The compounds appear to have been well tolerated, with effects limited to serum potassium increases after multiple dosing, particularly in a compound with an active metabolite [R15-0689].

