2. RATIONALE, OBJECTIVES, AND BENEFIT - RISK ASSESSMENT

2.1 RATIONALE FOR PERFORMING THE TRIAL

This is the second trial with BI 1265162 and the first with multiple dose administration. The objective of this trial is to investigate the safety, tolerability and pharmacokinetics of BI 1265162 in healthy male subjects. The chosen population of healthy volunteers using multiple rising inhalative doses is adequate to provide the basis for the phase 2 clinical development program of BI 1265162 in CF and COPD. This trial will provide pharmacokinetic information in healthy volunteers at steady state exposure.

The inclusion of male healthy volunteers as a trial population in phase I studies is ideal as they provide relatively stable physiological, biochemical and hormonal conditions (steady state) for studying drug effects. Healthy volunteers can be tested under standardised conditions in an environment which allows repeated testing.

In this multiple rising dose (MRD) study, within each dose group, all actively treated individuals will receive the same BI 1265162 dose. The next higher dose will only be administered (to the next group) if the treatment in the preceding dose groups was safe and showed acceptable tolerability.

Dose Selection

It is intended to investigate the following dose levels of BI 1265162 in the MRD part of this trial: 10, 30, 100, 300 and 600µg twice daily (bid) for Days 2-7 and single dose on Day 1 and 8. The background for this dose selection is described in the following.

Starting dose

Considering the favourable preclinical and clinical safety profile of BI 1265162, and taking into consideration other systemic and inhaled ENaC inhibitors which have been well tolerated, with known, easily monitorable and reversible side effects (changes in electrolytes), a sub-therapeutic dose of 10 µg bid has been selected as the starting dose in this MRD trial. This dose is within the range of ED50 (cf. Table 2.1: 1).

Maximum dose and dose escalation

As stated above, a minimum daily dose of approximately may be required to achieve therapeutic exposure to BI 1265162.

Trial Protocol Page 26 of 84

Proprietary confidential information © 2018 Boehringer Ingelheim International GmbH or one or more of its affiliated companies

However, higher doses might still be well tolerated while providing a larger magnitude of therapeutic effects.

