3. DESCRIPTION OF DESIGN AND TRIAL POPULATION

3.1 OVERALL TRIAL DESIGN AND PLAN

This multiple-rising dose trial is designed as double-blind, randomised, and placebocontrolled within parallel dose groups.

A total of 50 healthy male subjects is planned to participate in the trial, according to 5 sequential groups comprising 10 subjects per group. However, additional subjects may be entered to allow testing of additional doses on the basis of experience gained during the trial conduct, provided the planned and approved highest dose will not be exceeded. Thus, the actual number of subjects entered may exceed 50, but will not exceed 70 subjects entered. Such changes may be implemented via non-substantial CTP Amendments.

Within each dose group, 8 subjects will receive the active drug and 2 will receive placebo. Only one dose is tested within each dose group. Each dose group will consist of 2 cohorts (5 subjects each, 4 on active drug and 1 on placebo) which will be treated subsequently for safety reasons. The time interval between these cohorts will be at least 70 hours from first subject dosed.

The dose groups to be evaluated are outlined in Table 3.1: 1 below.

Table 3.1: 1 Dose groups

Dose Group	1	2	3	4	5	
Dose (µg) bid	10	30	100	300	600	
Number of subjects	10	10	10	10	10	
Subjects receiving placebo	2	2	2	2	2	
Subjects receiving active drug	8	8	8	8	8	

The dose groups will be investigated consecutively in ascending order of doses, maintaining a time interval of at least 5 days between the last drug administration in the previous dose group and the first drug administration of the subsequent dose group. The decision to proceed to the next dose group will be based upon the safety and tolerability of the preceding dose groups. The next dose will only be given if, in the opinion of the investigator, no safety concerns arose in the preceding dose group (i.e. no dose-limiting events occurred) and if none of the pre-specified trial-specific stopping criteria were met (refer to Section 3.3.4.2).

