A documented Safety Review must take place prior to each dose escalation. Furthermore, an unscheduled safety review meeting can be requested anytime for any reasonable cause by the Principal Investigator (or an authorised deputy) or the sponsor of the study, e.g. because of any unforeseen adverse events, etc. Dose escalation will only be permitted if no safety concerns exist in the opinion of the Principal Investigator (or an authorised deputy) and the trial clinical monitor (or an authorised deputy).

Although no formal Safety Review meeting will take place within a given dose group, safety will be continuously monitored during this trial, and an individual will only be dosed in the

Page 32 of 84

Proprietary confidential information © 2018 Boehringer Ingelheim International GmbH or one or more of its affiliated companies

absence of any safety concern (i.e. no dose-limiting events occurred) and if none of the prespecified trial-specific stopping criteria have been met (refer to Section 3.3.4.2).

The minimum data set for review consists of the following data:

- AEs in the current and preceding dose groups (including clinically relevant findings from ancillary safety testing listed below) (Note: AEs may be ongoing at the time of Safety Reviews and AE information may be subject to change prior to Database Lock)
- Results from 12-lead EGG in the current and preceding dose groups.
- Vital signs in the current and preceding dose groups
- Spirometry data
- Clinical laboratory tests in the current and preceding dose groups
- Check of criteria for stopping subject treatment as per Section 3.3.4.1

The decision to escalate the dose will be made jointly by the Principal Investigator (or an authorised deputy) and the trial clinical monitor (or an authorised deputy) after in-depth analysis of all available safety data, especially SAEs (if occurred), AEs and out-of-range laboratory results (if considered clinically significant). Safety Reviews can be conducted face-to-face or by video/telephone conference. The trial clinical monitor is responsible for organization and minutes of the reviews. Minutes will be signed off by the Principal Investigator (or an authorised deputy) and filed in the ISF and TMF.

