3.3.4.2 Discontinuation of the trial by the sponsor

Boehringer Ingelheim reserves the right to discontinue the trial overall or at a particular trial site at any time for any of the following reasons:

Proprietary confidential information © 2018 Boehringer Ingelheim International GmbH or one or more of its affiliated companies

- New toxicological findings or serious adverse events invalidate the earlier positive benefit-risk-assessment. Dose escalation will be terminated if more than 50% of the subjects at one dose level show drug-related and clinically relevant adverse events of moderate or severe intensity, or if at least one drug-related serious adverse event is reported.
- The expected enrolment goals overall or at a particular trial site are not met
- Violation of GCP, or the CTP or the contract with BI by a trial site or investigator, disturbing the appropriate conduct of the trial
- The sponsor decides to discontinue the further development of the investigational product.
- Dose escalation will be stopped as soon as at least 2 subjects at one dose level on active drug showed relevant individual QT prolongation, i.e. a QTc increase of greater 60 ms from baseline in connection with absolute QT or QTc greater than 500 ms, which has been confirmed by a repeat ECG recording.
- Dose escalation will be stopped as soon as at least 2 subjects at one dose level on active drug showed serum potassium levels > 5.5 mmol/L in non-hemolyzed blood

The investigator / the trial site will be reimbursed for reasonable expenses incurred in case of trial termination (except in case of the third reason).

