		176:00 to 180:00 (16:00 to 20:00)	
		180:00 to 192:00 (20:00 to 08:00 on Day 9)	

Descriptive statistics of laboratory data will be calculated by planned time point based on the worst value of the subject at that planned time point (or assigned to that planned time point).

For vital signs and spirometry, descriptive statistics will be calculated by planned time point based on the last value of the subject at that planned time point (or assigned to that planned time point).

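### The only laboratory frequency table named in the SAP uses the last on-treatment value, and no visible output counts subjects above the protocol's 5.5 mmol/L potassium limit

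*SAP*

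**What the plan says.** Protocol 3.3.4.2 stops dose escalation as soon as "at least 2 subjects at one dose level on active drug showed serum potassium levels > 5.5 mmol/L in non-hemolyzed blood". Potassium is the only laboratory value with a numerical escalation limit of its own. Protocol 1.2.5 describes inhaled compounds of the class as apparently well tolerated, "with effects limited to serum potassium increases after multiple dosing", and Protocol 2.1 calls the electrolyte changes reversible.

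SAP 7.8.2 names these laboratory outputs: descriptive statistics over time and for change from baseline, median electrolyte plots, exposure-response scatterplots for serum potassium and sodium, and one kind of frequency table: "Frequency tables of changes between baseline and last value on treatment with respect to the reference range will be presented". It adds: "Standard or project-specific rules for flagging clinically significant values in an automated manner will not be applied in this study". Clinical significance is left to the investigator and to the report planning and database lock meeting. Analyses use values normalised to a standard unit and reference range.

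Under SAP 6.7, laboratory statistics "will be calculated by planned time point based on the worst value of the subject at that planned time point", and an unscheduled repeat is assigned to the preceding scheduled time point. Neither 5.5 mmol/L nor haemolysis is mentioned in the visible SAP text.

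**The concern.** The protocol identifies potassium as the laboratory value to watch and gives it a limit. A reader of the report will want to know how many subjects at each dose passed that limit, compared with placebo. The named frequency table cannot answer this. It keeps one value per subject, probably the one furthest from dosing, and judges it against the reference range instead of the trial's limit.

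Two results could mislead. A rise during twice-daily dosing that has resolved by the last value appears as no shift. Conversely, if worst means highest for potassium, a haemolysed high result outranks its clean repeat at the same time point, so a printed maximum can look like an exceedance that the stopping rule would not count. Only a case-by-case decision at the database lock meeting would remove it.

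**Working it through.** The plan states no figure for this point. The check rebuilds the sampling schedule.

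**Inputs.** Doses (Flow Chart): 0 h; every 12 h from 24 h to 156 h; 168 h. In-house post-dose samples that include serum electrolytes (Flow Chart and its footnote 13) are below. Time since dose = sample time minus last preceding dose time.

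| Sample | Preceding dose | Time since dose |
|---|---|---|
| Day 1, 2:00 | 0:00 | 2 h |
| Day 2, 23:55 | 0:00 | 23.9 h |
| Day 3, 50:00 | 48:00 | 2 h |
| Day 4, 74:00 | 72:00 | 2 h |
| Day 6, 122:00 | 120:00 | 2 h |
| Day 8, 167:55 | 156:00 | 11.9 h |
| Day 8, 170:00 | 168:00 | 2 h |
| Day 9, 192:00 | 168:00 | 24 h |

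Five of the eight samples are at 2 h.

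**Which sample is the last on-treatment value?** SAP Table 6.1: 1 ends the phase, exclusively, at last dose + REP, or at trial termination if earlier. The REP is blacked out, so it is varied, for a completer on scheduled samples:

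- REP up to 2 h: last value 167:55; 0 of 5 enter.
- REP above 2 h and up to 24 h: last value 170:00; 1 of 5 enters.
- REP above 24 h: last value 192:00, or possibly the end-of-trial sample if the REP exceeds 48 h; 0 of 5 enter.

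A footnote to that table, which speaks of trial termination within 2 days of the last dose, points to the third case. A subject who stops early contributes at most one. So at least 4 of 5 are outside the table for every subject, whatever the REP.

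**Named outputs that count subjects above 5.5 mmol/L:** none in SAP 6.1, 6.7, 7 or 7.8.

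**What the stopping rule leaves unreported.** One active subject of 8 above the limit does not trigger it. Across the four lower dose groups, up to 4 × 1 = 4 of 32 (12.5%) could exceed the limit without stopping escalation.

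**Illustration (invented data).** Suppose 2 of 8 exceed the limit on Days 3 to 6 only: 25%, exact 95% CI 3.2% to 65.1%. The last-value table would show 0 of 8 shifted high, CI 0% to 36.9%. The documents do not allow an estimate of how often this would happen.

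**Cost of using the highest of eight.** Assume each sample has a 2.5% chance of lying above the range with no drug effect. With independent samples, the chance that at least one does is 1 − 0.975^8 = 18.3%. With equicorrelated normal values it is 12.5% at within-subject correlation 0.5 and 6.0% at 0.9. In 10 placebo subjects that is 1.8, 1.3 or 0.6 expected, against 0.25 with one sample.

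**The case against.** The strongest reply is that the data are not lost. All five 2 h samples enter the time-point statistics, which print the maximum, as well as change from baseline and the median plots. The Day 1 and Day 8 samples also enter the scatterplots. Every value is listed, and Protocol 7.3.3 highlights those out of range. That stands: a reader who infers that the 2 h samples go unused would be wrong. What is missing is a count. A maximum shows that someone was high but not how many subjects were, and it is on the normalised scale.

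Secondly, a reader might infer that subjects are less protected, especially at 600 µg, after which no escalation remains. The documents do not support this. Protocol 3.1 states that "A documented Safety Review must take place prior to each dose escalation". Within a dose group, it allows an individual to be dosed only if no stopping criterion has been met, and Protocol 2.3 requires laboratory results to be evaluated before each subject and the next cohort. These provisions apply at 600 µg too.

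Thirdly, masking is assumed. Steady state is predicted by 4 to 5 days, so a drug-driven rise may well persist to Day 8, and reversible carries no recovery time. This stands as a limit on size. It does not rescue the table, because with a REP above 24 h the value used is from Day 9 or later, at least 24 h after the last dose.

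Fourthly, the sponsor's laboratory standard (SAP reference 9) may add tables, and a high potassium judged clinically relevant reaches the adverse event tables. Both are fair. The second depends on judgement, not on the limit. The sentence against automated flagging concerns labels of clinical significance; it should not be read as forbidding a threshold count.

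Finally, the highest of eight compared with one baseline value favours upward shifts. This stands, and is a reason to keep the last-value table alongside.

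**Conclusion.** The point holds as a minor final-reporting weakness. At most one of the five 2 h potassium samples can enter the only named laboratory frequency table, and none does for completers if the REP exceeds 24 h. No visible output counts subjects above the trial's own limit. The first statement rests on the Flow Chart and does not depend on the blacked-out REP. The second covers visible text only: it does not establish that the report will lack such a count. The haemolysis point further assumes that worst means highest for potassium, which SAP 6.7 does not define. How often a rise would be hidden is unknown.

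**What to change.** In SAP 7.8.2, for serum potassium only:

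- Report n (%) of subjects with any non-haemolysed on-treatment value above 5.5 mmol/L on the measured scale, scheduled or repeat, by dose group and for pooled placebo.
- Present the shift from baseline to the highest non-haemolysed on-treatment value. The last-value table may stay beside it.

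In SAP 6.7, leave potassium results from haemolysed blood out of the worst-value selection, list them, and use the clean repeat where there is one.

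The other laboratory tables, adverse event recording, the primary endpoint and the stopping rule stay as they are. No extra samples or visits are needed. No document names a database field for haemolysis, so status must be captured, perhaps retrospectively, for potassium results above the upper reference limit. The highest-value table will show more chance exceedances (6.0% to 18.3% of subjects against 2.5%, under the assumed 2.5% per sample), so a note should direct the reader to the pooled placebo column.
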